#### 6.4 Appendix 4: Tipping point analysis

A tipping point analysis will be applied by applying an unfavorable additive shift (referred to as delta adjustment) to values imputed to fill in the missing and unobservable data that occur in presence of ICEs. Delta adjustment will be applied only to imputed values in the elinzanetant arm. No delta adjustment will be applied to missing values that occur outside of the time frame of any ICE. The following steps will be implemented for primary endpoint, i.e., frequency of HF:

1. The imputation step will be done as described in Section 5.3.1.
2. Prior to the analysis step, each imputed value in the elinzanetant arm that occurs in the time frame of an ICE would have a value of “delta” added to it (see Section 5.3.2.2 for settings of delta for each type of endpoint). The same value of delta will be applied at each time point.
3. Observed, imputed, and adjusted data will be analyzed, and results combined as described in Section 5.3.1.
4. Steps 1-3 will be repeated with increasing settings of “delta” (see Section 5.3.2.2) for primary endpoint until the estimated treatment difference at Week 12 is no longer statistically significant at the 0.025 one-sided level. The corresponding “delta” setting will be selected as the tipping point for that endpoint.

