**Figure 1–1: Study schema**

- This is a multi-center, multi-country, double-blind, randomized, parallel-group, placebo-controlled, Phase 3 intervention study in post-menopausal women with VMS.
- Primary efficacy endpoint will be evaluated at Week 12.
- Total study duration for all participants: approximately 62 weeks (plus potential washout period), including
  - Washout (if applicable)
  - Screening approximately 6 weeks
  - Treatment: 52 weeks
  - Follow-up: 4 weeks
- Eligible participants will be randomized 1:1 into two arms as follows:
  - elinzanetant
  - placebo
- Randomization will be stratified by region: North America, rest of the world (ROW)
- No interim analysis is planned.
- Primary analysis will be performed after database release after last patient last visit (LPLV).

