### 3. Sample Size Determination

Approximately 600 participants will be randomly assigned to study intervention. Of these, 300 participants will be randomly assigned to elinzanetant and the other 300 participants will be randomly assigned to the placebo arm. Assuming a yearly drop-out rate of 30 % and 10% during the months 1-3 and 4-6 in the elinzanetant arm, approximately 210 participants will be available that were treated for 1 year and approximately 240 participants will be available that were treated for at least 6 months.

The number of participants needed for this study is based on the total number of participants needed for the safety evaluation. Following the ICH E1 guideline ([EMA 1995](#)), a total of 1500 participants are required that were exposed to at least one dose of elinzanetant 120 mg. Of these 1500 participants 300-600 should have been treated for at least 6 months and approximately 100 for 1 year. Based on the number of participants that are available from previous phase 1 and phase 2 studies, together with the number of participants that are planned to be enrolled in upcoming phase 3 studies, the number of participants needed for the elinzanetant arm in this study is 300, also taking into account the assumed drop-out described above.

Assuming a screen failure rate of 30% approximately 860 participants need to be enrolled to achieve the required number of 600 randomized participants. Additionally, further participants may be enrolled in case of an exceptionally high drop-out rate due to a trial-continuity issue.

A formal sample size justification was performed for the primary efficacy endpoint using the one-sided two-Sample T-test (equal variance) assuming at least approximate normal distribution. Drop-out rate during the first 3 months is assumed to be 10%. The power with treatment differences (i.e. mean change in frequency of moderate to severe HFs from baseline to Week 12), with N=270 per treatment group and assumed standard deviation are provided in [Table 3-1](#). The data from placebo arm in SWITCH-1 study ([NCT03596762, 2020](#)) was used for assumption of standard deviation.

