## 5. Statistical Analyses

### 5.1 General Considerations

All variables collected in the study will be summarized using descriptive statistical methods. Continuous variables will be summarized using at least the following descriptive statistics: number of non-missing observations, arithmetic mean and standard deviation (SD), median, minimum and maximum. The geometric mean and geometric SD will be provided instead of the arithmetic mean and SD for variables where lognormal distributions are assumed. Categorical data will be summarized using frequency tables. Where appropriate, the data will also be presented by visit or week, including the analysis of the changes from baseline.

For the main analysis the type I error rate will be controlled at 2.5 % one-sided. Where appropriate two-sided 95 % confidence intervals (CIs) will be provided.

The statistical evaluation will be performed by using the software SAS (release 9.4 or higher; SAS Institute Inc., Cary, NC, USA).

Variables recorded in the electronic case report form (eCRF) and relevant derived variables will be shown in subject data listings, whereby only randomized participants will be included. Data from screening failures will only be shown in the 'Screening failure' listing.

Number of decimal places for summary statistics are shown in [Table 5–1](#). Derived variables would have maximum 1 decimal place and that value is considered as original data.

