SAS code:	<pre>PROC MIXED data=DATA;   CLASS subject treatment region week;   MODEL change = baseline treatment region week     treatment*week baseline*week/ddf=KR outp=resid s;   REPEATED week / subject=subject type=un;   RANDOM subject; /* only if AR(1) covariance structure is used */   LSMEANS treatment*week /cl diff;   ESTIMATE 'Elinzanetant - Placebo at Week 12' treatment 1     -1 treatment*week 0 0 0 1 0 0 0 -1 /cl;   ODS OUTPUT TESTS3=TYPE3_eff LSMeans=LSMEAN   ESTIMATES=ESTIM;   RUN;</pre>

A treatment policy strategy will be applied to handle all of the ICEs in this trial in the main estimand. According to this policy, all collected data should be utilized in the analysis irrespective of occurrence of the ICEs.

Although all study participants are expected to be followed after ICEs, some missing data may occur. Missing values that occur while participants continue on their randomized treatment and simply represent missed assessments will be assumed missing at random (MAR). Such missing values are likely to be intermittent and will be imputed using a Monte Carlo Markov Chain (MCMC) MI method for imputation of non-monotone missing data. For the baseline value to be imputed, at least 2 post-baseline values out of the 4 post-baseline values (i.e. Week 1, 4, 8 & 12) need to be available. Possible missing baseline values will be

imputed together with intermittent missing values. Absolute values will be used for imputation steps.

Missing values that occur after the discontinuation of randomized treatment will be imputed using a multiple imputation (MI) model (Rubin, 1987) such that it aligns with the treatment policy estimand. The MI regression model will include auxiliary variables indicating (yes/no) whether the participant continued on randomized treatment at each visit (i.e. Week 1, 4, 8 & 12). These variables will be included in the imputation model to account for the occurrence of permanent discontinuation of randomized treatment (Guizzaro et al., 2021). In addition to the indicator variables, baseline HF, region and treatment as specified in [Table 5–3](#) as well as previous post-baseline endpoint values will also be included in the imputation model. In case, there are less than 10 participants (who permanently discontinued the randomized treatment) across both treatment groups with available post-discontinuation data at any intermediate time point, the indicator variable will not be included in the imputation model for that time point.

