### 5.3.2.2 Tipping point analysis

A tipping point analysis will be applied to assess the sensitivity of the main analysis results to modeling of the missing and unobservable data that occur in presence of ICEs as described in Section 5.3.1. This will be done by applying an unfavorable additive shift (referred to as delta adjustment) to the values imputed by the MI model for the main analysis in the elinzanetant arm. For the endpoint related to the frequency of HF, the adjustments will be applied with delta values of 1, 2, 3, 4, etc. in each successive tipping point iteration until a tipping point is attained. Additional details on the tipping point sensitivity analysis are provided in Section 6.4.

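### The tipping-point run leaves missed diary weeks outside an intercurrent event at their missing-at-random values, and the SAP does not settle how many Week 12 values that covers

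*SAP*

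**What the plan says.** SAP 5.3.1 makes two assumptions about missing data. After discontinuation of randomized treatment, values come from a multiple-imputation model with on-treatment indicators. For the rest, "Missing values that occur while participants continue on their randomized treatment and simply represent missed assessments will be assumed missing at random (MAR"). The SAP expects these to be mostly intermittent and imputes them by MCMC.

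SAP 5.3.2.2 and 6.4 define the tipping-point analysis. In 6.4, "each imputed value in the elinzanetant arm that occurs in the time frame of an ICE would have a value of" delta added, and the exclusion is explicit: "No delta adjustment will be applied to missing values that occur outside of the time frame of any ICE". On the grid, 5.3.2.2 says "the adjustments will be applied with delta values of 1, 2, 3, 4, etc. in each successive tipping point iteration", continuing until significance is lost.

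Three other rules bear on which values are shifted:

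- **ICEs** (SAP Table 1–2): temporary treatment interruption, permanent discontinuation, and prohibited medication with an impact on efficacy.
- **Missing week** (SAP 5.1.1.1.1 and 5.1.2.1): a diary day is lost only if both its evening entry and the next morning's entry are absent. A week is missing when more than two days are lost.
- **Week 12 interruption flag** (SAP 6.5.1): intake on fewer than 5 of 7 days in weeks 11–12, or below 80% over weeks 1–12, computed from the eDiary intake record. Protocol 6.4 has that record completed with the evening diary.

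**The concern.** The outcome is self-reported in a diary, so whether a woman completes it in a given week may depend on her symptoms that week. MAR cannot be checked from the data, and a sensitivity analysis is the place to vary it.

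The other planned analyses do not. The rank ANCOVA in SAP 5.3.2.1 is run on the same imputed datasets, and both supplementary analyses keep MAR for missed assessments outside an ICE (SAP 5.3.3.1, carried over to 5.3.3.2). Nor does the expectation of intermittent missingness help much at the primary time point. Week 12 is the last of the four visits in the imputation model, so a missing Week 12 value has no later modelled value to anchor it.

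At stake is what the reported tipping delta means. If elinzanetant Week 12 values exist outside any ICE, they stay at their MAR imputations however large delta becomes, and the delta needed to lose significance is larger than if all imputed values were shifted.

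**Working it through.** **Inputs from the documents.** SAP 5.1: "For the main analysis the type I error rate will be controlled at 2.5 % one-sided". SAP 1.2: "Eligible participants will be randomized 1:1 into two arms as follows", with 300 per arm. SAP 3: "Drop-out rate during the first 3 months is assumed to be 10" per cent, so 300 × 0.90 = 270, and power "with N=270 per treatment group and assumed standard deviation are provided in" Table 3–1, where the SD is 4.29.

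**Inputs assumed.** The documents do not give f or m. I take f = 10%, with 5% as a variant, and m = 1%, 2% and 5%.

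**Step 1: reproduce the plan's figure.** SE = 4.29 × √(2/270) = 0.369. A noncentral t with 538 degrees of freedom at one-sided 0.025 gives power of 77.1%, 98.2% and 99.97% for differences of 1.0, 1.5 and 2.0. Table 3–1 is reproduced. The critical difference is 1.96 × 0.369 = 0.72 hot flashes per day.

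**Step 2: which missing Week 12 values fall inside an ICE?** A missing week needs at least three days with neither entry, so evening entries exist on at most 7 − 3 = 4 days. Enumerating all evening/morning patterns over seven days confirms this: 3991 patterns make the week missing, and all 3991 have evening entries on fewer than 5 days. Intake is documented with the evening diary, which leaves two readings:

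- An undocumented day counts as not taken. The woman meets the Week 12 interruption rule, her value lies inside an ICE, and delta is added.
- An undocumented day is ignored or treated as compliant. A woman who takes the drug and skips the diary is not flagged, and delta is never added.

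**Step 3: effect on the tipping delta under the second reading.** Let d be the size of the observed difference and s the shifted share of the elinzanetant arm at Week 12. The tipping delta is the smallest δ with (d − sδ)/SE(δ) < 1.96, where SE(δ)² = 2 × 4.29²/270 + s(1 − s)δ²/270. The planned run has s = f; shifting all imputed values has s = f + m.

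Checks at d = 1.5:

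- s = 0.10, δ = 7.31: (1.5 − 0.731)/√(0.1363 + 0.0178) = 0.769/0.393 = 1.96.
- s = 0.15, δ = 4.98: (1.5 − 0.747)/√(0.1363 + 0.0117) = 0.753/0.385 = 1.96.

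With f = 10%:

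| Difference | As planned | m = 1% | m = 2% | m = 5% |
|---|---|---|---|---|
| 1.0 | 2.70 | 2.46 | 2.26 | 1.82 |
| 1.5 | 7.31 | 6.68 | 6.16 | 4.98 |
| 2.0 | 11.65 | 10.68 | 9.85 | 8.01 |
| (f + m)/f | 1.0 | 1.1 | 1.2 | 1.5 |

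On the SAP's integer grid, the reported value at a difference of 1.5 goes from 8 to 7, 7 and 5. At 1.0 it goes from 3 to 3, 3 and 2.

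With f = 5% and a difference of 1.5, delta goes from 13.84 to 11.73, 10.19 and 7.31.

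**Step 4: effect on the estimate.** If on-treatment missing values are truly worse by δ, the difference is overstated by mδ. For δ of 1 to 4 this is 0.02–0.08 hot flashes per day at m = 2% and 0.05–0.20 at m = 5%.

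These are approximations: no baseline adjustment and no between-imputation variance.

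**The case against.** The strongest reply is that the gap may be nearly empty. By Step 2, every woman with a missing Week 12 diary has too few evening entries to document intake on 5 of 7 days. The companion 80% rule in SAP 6.5.1 divides capsules taken by a fixed 168, so an undocumented day adds nothing to the numerator but stays in the denominator. That favours reading undocumented as not taken. This stands as a real possibility, but the day-level rule is not written down. Intake is also a separate item on the device (Protocol 8.1.1), and SAP 5.3.1 and 6.4 both provide for missing values outside an ICE.

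A reader might infer that MAR for women still on treatment is never stress-tested. The documents do not support that. Interruption and prohibited medication occur in women on treatment, and their imputed values are shifted. Withdrawal, loss to follow-up and non-compliance are listed discontinuation reasons in SAP 6.5.2, so missing values after discontinuation for those reasons are shifted too.

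It is also fair that SAP 5.3.2.2 openly confines its aim to data missing in the presence of ICEs, so the planned delta answers its stated question correctly. Single-entry days, tolerance of two lost days, retrospective entry and site warnings should keep missed weeks few. None of this supplies a test of MAR for the values that remain.

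**Conclusion.** The exclusion is explicit, and no other planned analysis tests MAR for missed diary weeks outside an ICE. Whether this leaves a material gap at Week 12 turns on the unstated treatment of undocumented intake days.

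If such values exist, the direction is certain: the planned tipping delta is larger than the all-missing-data one, by about (f + m)/f. With f = 10% and m = 1–5% assumed, that is about 1.1–1.5. At m of 1–2% it is small and may vanish on the integer grid.

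A reader might go further and attach a fixed percentage of overstated robustness to this trial. The documents do not support one, because any such figure only restates the assumed f and m. At a difference of 1.5 and f = 10%, even the 5.0 reached at m = 5% exceeds the planning SD of 4.29, so the conclusion would probably not change. At a difference of 1.0, a fall from 2.7 to 1.8 could matter more.

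The point concerns how robustness is read, not the validity of the primary test.

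**What to change.** In SAP 6.4:

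1. Keep the planned run as it is.
2. Add a second run on the same delta grid that adds delta to every imputed post-baseline elinzanetant value, inside or outside an ICE. Imputed baselines stay unshifted.
3. Report both tipping points, with the number of Week 12 values imputed inside and outside ICEs by arm, so that f and m can be seen.

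A sentence in 6.5.1 saying how a day without an intake record counts would make the split between inside and outside reproducible.

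The cost is a few sentences, one more pass over imputed datasets that already exist, and a possibly less favourable tipping delta. The primary estimate does not change. If few values lie outside ICEs, the two tipping points will nearly agree and the question is closed.

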## 6.5 Appendix 5: Details regarding the identification of intercurrent events

### 6.5.1 Temporary treatment interruption

Per definition (see Section 1.1), the ICE “temporary treatment interruption” will only be considered for week 1, week 3 and 4, week 7 and 8, and week 11 and 12. Specifically, temporary treatment interruption is defined as

- Treatment taken on <5/7 days during week 1 for Week 1
- Treatment taken <80% during weeks 1-4 OR treatment taken on <5/7 days during either week 3 or 4 for Week 4
- Treatment taken <80% during weeks 1-8 OR treatment taken on <5/7 days during either week 7 or 8 for Week 8
- Treatment taken <80% during weeks 1-12 OR treatment taken on <5/7 days during either week 11 or 12 for Week 12.

The criterion for treatment taken on 5/7 days during the corresponding two weeks, as defined above, is met, if in any selected 7 consecutive days within those weeks, the treatment has been taken for less than 5 days (i.e., at least 3 missed intakes). If the criterion is met, an ICE flag will be placed for the corresponding visit week for HFDD.

To identify whether < 80 % treatment was taken, planned compliance during weeks 1-4 will be calculated as

$$100 * \text{Number of capsules taken} / 56$$

where 56 is based on two tablets per day over 28 days. Planned compliance during weeks 1-8 will be calculated as

$$100 * \text{Number of capsules taken} / 112$$

where 112 is based on two capsules per day over 56 days.

Planned compliance during weeks 1-12 will be calculated as

$$100 * \text{Number of capsules taken} / 168$$

where 168 is based on two capsules per day over 84 days.

To calculate the number of days per week with treatment intake, a day where at least one capsule was taken, will be considered as a day with treatment intake.

For the identification of the ICE temporary treatment interruption, the compliance and daily treatment intake will be calculated based on the ePRO instrument ‘Study drug intake documentation’.

Regarding the reasons, AEs that lead to a treatment interruption, together with start and end date, will be collected on the respective eCRF page. Similarly, reasons related to COVID-19 or administrative reasons will also be collected in the eCRF.

The reasons for temporary treatment interruption will be reviewed during blind review of the data. The observed temporary treatment interruptions together with the corresponding reason will be presented in data listings.

### **6.5.2 Permanent discontinuation of randomized treatment**

The reasons for permanent discontinuation of randomized treatment will be collected on the corresponding eCRF page, among others with AE or lack of efficacy as possible options. A permanent discontinuation of randomized treatment will be considered to be due to “other treatment unrelated reasons” if AE or lack of efficacy was not selected as reason and any of the following was selected:

- Non-compliance with study device
- Site terminated by sponsor
- Technical problems
- Pregnancy
- Subject decision
- Subject decision: unwillingness to comply with study procedures
- Lost to follow-up
- Other
- COVID-19 pandemic related: subject specific
- COVID-19 pandemic related: other
- Non-compliance with study drug
- Randomized by mistake
- Withdrawal by subject

The observed permanent discontinuations of randomized treatment together with corresponding reason will be presented in data listings.

Discontinuation due to AE or lack of efficacy may be handled differently depending on estimand for participants who remained untreated/background therapy and for participants who initiate alternative VMS treatment. The treatment status (i.e., remained untreated/on background therapy vs. initiate alternative VMS treatment) should be captured for all participants who discontinued from randomized drug irrespective of the reason for

discontinuation.

**Table 6–3: Preliminary list of alternative VMS treatment by drug grouping (can be updated during blind review meeting)**

DGCODEL0	DGNAME0	DGCODEL1	DGNAME1	DGCODEL2	DGNAME2	Duration of impact with respect to efficacy* (considered up to 12 weeks**)
		5	Hormone replacement therapy	2	Oestrogens	1, From 1st dose to 4 weeks after the last dose if the route is vaginal, intravaginal, cutaneous, nasal or transdermal. 2, From 1st dose to 8 weeks after the last dose if the route is oral, sublingual or intrauterine, 3, From 1st dose to 12 weeks or longer if the route is subcutaneous or intradermal.
		5	Hormone replacement therapy	3	Progestogens	1, From 1st dose to 4 weeks after the last dose if the route is vaginal, intravaginal, cutaneous, nasal or transdermal. 2, From 1st dose to 8 weeks after the last dose if the route is oral, sublingual or intrauterine, 3, From 1st dose to 12 weeks or longer if the route is subcutaneous or intradermal.
1633	Drugs for psychiatric disorders	111	Antidepressants	113	Selective serotonin reuptake inhibitors (SSRI)	From 1st dose to 4 weeks after the last dose

\*In this column, the terms "1st dose" and "last dose" both refer to the start date and stop date of certain doses of concomitant medication. If the dose was changed, a new start date and/or stop date were reported.

\*\* No further differentiation if duration of impact is longer than 12 weeks since ICEs are considered in the analysis only for the first 12 weeks of the study.

**Table 6–4: Preliminary list of alternative VMS treatment by drug names (can be updated during blind review meeting)**

WHO Drug Name	WHO Drug Record Number	WHO Drug Sequence Number 1	WHO Drug Sequence Number 2	Duration of impact with respect to efficacy* (considered up to 12 weeks**)
OXYBUTIN	005389	02	057	From 1st dose to 4 weeks after the last dose

\*In this column, the terms "1st dose" and "last dose" both refer to the start date and stop date of certain doses of concomitant medication. If the dose was changed, a new start date and/or stop date were reported.

\*\* No further differentiation if duration of impact is longer than 12 weeks since ICEs are considered in the analysis only for the first 12 weeks of the study.

Although more alternative treatment options may be available, only drug groupings/ drug names are listed that were reported in OASIS 1-3 studies as of finalization of this statistical analysis plan.

